#### F. Statistical Considerations:

**F1. Randomization and blinding:** Patients will be randomized (1:1:1) to one of the three ACT target groups (low, medium, or high) using a dynamic minimization algorithm so as to optimize the likelihood that balance between the low, medium, and high ACT target groups will be

achieved with respect to sex (male or female) and glomerular filtration rate (30 to 59 ml/min/1.73m^2 or ≥60 ml/min/1.73m^2). The algorithm will be implemented in RAVE RTSM, a secure web-based interface, and accessed by the study coordinator or other appointed study personnel. Randomization will be conducted after the diagnostic portion of the procedure on only patients who will require ACT monitoring. Since eligible patients will require ACT monitoring during PCI, we will not conduct the study in a strictly blinded fashion. However, study participants will not be informed of their randomization assignment.

**F2. Data collection and handling:** Electronic case report forms along with a corresponding secure REDCap database will be created for data collection (29). Data to be collected will include baseline demographics, comorbidities, procedural variables, in-hospital events, NACE component, and adverse events.

**F3: Definition of study outcomes:** Study endpoints are summarized in Appendix II.

**F3.1 Primary study endpoint:** Our **primary study endpoint is bleeding** and is defined as either a Bleeding Academic Research Consortium (BARC) hemorrhage grade of 1, 2, 3, or 5 or an EASY hematoma scale grade of I-V from the time of PCI to the time the patient is discharged from the hospital.

**F3.2 Primary safety endpoint:** Our **primary safety endpoint is a composite of net adverse clinical events (NACE) and stent thrombosis**, as defined by the Academic Research Consortium, from the time of PCI to the time the patient is discharged from the hospital.

**F3.2.1 NACE** is the composite of all-cause mortality, myocardial infarction (MI), stroke, target lesion revascularization, and major bleeding within 30 days after PCI.

**F3.2.2 MI** will be defined as any two of the following 3 criteria: 1) chest pain for at least 20 minutes; 2) elevation of cardiac biomarkers, preferably troponin, above the laboratory upper limit of normal; and 3) new pathological Q wave on electrocardiogram.

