Baseline patient and procedure characteristics of the three groups will be reported as number and percentage for categorical variables and median and interquartile range for continuous variables. To evaluate the possibility of imbalance, we will make comparisons between the three randomized groups using a Kruskal-Wallis test for ordered or numeric variables and a chi-square test (or Fisher's exact test) for categorical variables. For those baseline characteristics with imbalance between groups, we will summarize the number and percentage as well as relative risk and 95% confidence intervals as was done with the pre-planned analyses of sex, access site, and concomitant use of glycoprotein (GP) IIb/IIIa inhibitors with stratification by the baseline characteristic. In addition, we will use a multivariable logistic regression model with in-hospital bleeding as our outcome measure and fixed effects for group (reference group = low ACT target), sex, access site, concomitant use of glycoprotein (GP) IIb/IIIa inhibitors, and any other baseline characteristics with evidence of potential imbalance between groups (p-value  $\leq 0.20$ ) allowing no more than one variable for every 10 patients who experience in-hospital bleeding.

F5.4 Exploratory analysis plan: We will explore the association of ACT target with individual components of bleeding and NACE using a Cochran-Armitage trend test and report the number and percent of patients with each component separately for each group. Adjustment for multiple testing will be conducted using the Holm step-down method.

F5.5 Interim analysis plan: A blinded review of the study's overall incidence of the primary study outcome and the primary safety endpoint will be planned after 50% of patients have completed the study. If this review suggests that assumed incidence used to plan the study is much higher than the actual event rate then we may reestimate the sample size to ensure the study is adequately powered. Since the analysis will be conducted blind to group assignment this will not introduce statistical bias and adjustment to the study's significance level is not required...

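### F5.3 chooses extra covariates for the secondary adjusted bleeding model by baseline p-value, so chance fills it and GFR, a minimisation factor, almost never enters

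*Combined protocol and SAP*

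**What the plan says.** Section F1 allocates patients 1:1:1 by minimisation, seeking balance "with respect to sex (male or female) and glomerular filtration rate", with GFR split into 30 to 59 and 60 or above. It does not give the probability with which the preferred arm is assigned.

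Section F5.3 tests baseline characteristics between arms: "we will make comparisons between the three randomized groups using a Kruskal-Wallis test for ordered or numeric variables", and chi-square or Fisher tests for categorical ones. It then describes a multivariable logistic model for in-hospital bleeding with "fixed effects for group (reference group = low ACT target), sex, access site, concomitant use of glycoprotein (GP) IIb/IIIa inhibitors", to which it adds "any other baseline characteristics with evidence of potential imbalance between groups" (p ≤ 0.20), "allowing no more than one variable for every 10 patients who experience in-hospital bleeding". GFR is not among the fixed terms. There is no list of candidate characteristics and no order of entry under the cap. The same imbalance check also triggers stratified tables for any characteristic found unbalanced.

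Section F5.2 settles the primary aims without this model: pairwise chi-square or Fisher tests at 0.025 (Aim 1), Wilson intervals (Aim 2) and a Newcombe interval (Aim 3).

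**The concern.** In a randomised comparison, a baseline difference between arms is a chance event. Its p-value does not say whether the variable predicts bleeding, which is the reason to adjust for it. A screen on that p-value therefore makes the model depend on the accidents of one allocation. If more variables qualify than the cap allows, someone must choose among them, with outcome data in hand and no written rule.

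The screen also works against GFR. Minimisation exists to make GFR balanced, so a test for imbalance will almost always reject it. The model keeps sex, one allocation factor, and loses the other, and the plan gives no reason. At stake is the plan's only multivariable check on its primary outcome: two analysts could follow F5.3 faithfully and report different adjusted estimates.

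**Working it through.** **Inputs from the documents.** 504 patients, so 168 per arm; planned bleeding 5%, 15% and 25% (low, medium, high); 0.025 two-sided per comparison (F.4). Minimisation on sex and GFR stratum (F1). Screen at p ≤ 0.20 and a cap of one variable per 10 bleeds (F5.3).

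**Assumed, not in the documents.** 30% women; 30% with GFR 30–59 (15% and 45% also tried); preferred-arm probability 0.5 to 1.0; number and independence of candidate covariates; strength of GFR as a predictor of bleeding.

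**1. The plan's own figure.** Power for 5% v 15% is Φ[(0.10√168 − 2.241√(2 × 0.10 × 0.90)) / √(0.05 × 0.95 + 0.15 × 0.85)] = Φ[(1.296 − 0.951)/0.418] = Φ(0.825) = 79.5%. Simulation with the uncorrected chi-square test (20,000 runs) gives 81.0%, and more than 99.9% for 5% v 25%. This reproduces the stated power of more than 80%, so these rates are a fair basis for the event count.

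**2. Places under the cap.** Expected bleeds are 168 × (0.05 + 0.15 + 0.25) = 75.6, and 75.6/10 allows 7 variables. Arm, sex, access site and GP IIb/IIIa use are 4 variables, leaving 3 places. The standard deviation of the event count is 7.8, so one standard deviation either way (67.8 to 83.4) moves the cap between 6 and 8.

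**3. Chance entry.** Each non-minimised variable passes with probability about 0.20. With k independent candidates, 0.20k pass on average and P(at least one) = 1 − 0.8^k. More than 3 qualifiers exceed the places left; P(4 or more) = P(3 or more) − P(exactly 3).

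| k (assumed) | Mean passing | P(≥ 1) | P(≥ 4) |
|---|---|---|---|
| 10 | 2 | 89% | 0.322 − 0.201 = 12% |
| 15 | 3 | 96% | 0.602 − 0.250 = 35% |
| 20 | 4 | 99% | 0.794 − 0.205 = 59% |

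**4. GFR under minimisation.** With three arms, p ≤ 0.20 needs a chi-square (2 df) of at least −2 ln 0.20 = 3.22. With 30% low GFR, about 50 patients per arm, counts of 43/50/57 give 98/50 + 98/118 = 2.79 (p = 0.25). Counts of 42/50/58 give 128/50 + 128/118 = 3.64 (p = 0.16). So a spread of about 16 patients is needed. Simulated minimisation (400 trials per setting, 30% low GFR) gave:

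| Preferred-arm probability | Mean spread of low-GFR counts | GFR category at p ≤ 0.20 |
|---|---|---|
| 0.7 to 1.0 | 0.7 to 1.8 | 0% |
| 0.6 | 3.0 | 0.5% |
| 0.5 | 7.7 | 10.5% |
| Simple randomisation (4,000 trials) | – | 20% |

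At 0.8, the result was also 0% with 15% or 45% low GFR. If GFR were tested as a continuous variable by Kruskal-Wallis, it passed in 0.5% to 8% of trials at 0.7 to 1.0, 3.5% at 0.6 and 13% at 0.5.

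**5. Effect of leaving GFR out.** Medium v low, 800 trials per setting, preferred-arm probability 0.8, sex odds ratio 1.5 assumed:

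| GFR odds ratio (assumed) | SE without → with GFR | Power at 0.025 without → with GFR |
|---|---|---|
| 1.5 | 0.429 → 0.429 | 81.1% → 81.2% |
| 2 | 0.419 → 0.422 | 79.5% → 80.5% |
| 3 | 0.409 → 0.414 | 83.0% → 83.9% |

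Without GFR, the model SE did not exceed the empirical SD of the estimate (0.429 v 0.451, 0.419 v 0.426, 0.409 v 0.412). In a separate run of 300 trials at a GFR odds ratio of 3, the median odds ratio was 3.61 without GFR and 3.81 with it. Across all runs the power cost was about 0 to 2 points.

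**6. A fixed model.** Arm (2 df), sex, GFR stratum, access site and GP IIb/IIIa use are 5 variables and 6 df, with 75.6/6 = 12.6 events per df. At an assumed pooled rate of 12%, 0.12 × 504 = 60.5 bleeds give a cap of 6, and the model still fits.

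**The case against.** The strongest reply is that nothing decisive rests on this model. Aims 1 to 3 are settled by the F5.2 analyses. The logistic model is secondary, has no significance threshold of its own, and follows the imbalance checks as an addition. Admitting true baseline covariates by chance does not in itself bias a randomised comparison. If conditioning on allocation factors is the principle, F5.2 conditions on neither sex nor GFR. All of this stands, and it limits the point to a secondary analysis.

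Four stronger readings are tempting, and the documents do not support them.

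- A reader might infer that omitting GFR makes the error bars too wide. The model is logistic, and step 5 shows the standard error unchanged or slightly smaller without GFR. The documents also do not say how strongly GFR predicts bleeding.
- A reader might infer that GFR can never enter. That depends on the random element of the minimisation and on whether GFR is tested as a category or a number, and the plan states neither.
- A reader might count only 2 places left by counting arm as two terms. The cap is written in variables, which leaves 3.
- A reader might infer that the primary conclusions or the type I error of Aim 1 are at risk. They do not use this model.

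It is also fair to object that a model meant to be clean should not adjust for GP IIb/IIIa use without comment. Section D excludes use in the previous 72 hours and allows for provisional use, and F1 randomises after the diagnostic portion. Actual use can therefore follow randomisation and could be affected by arm. The fix takes this into account.

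**Conclusion.** The point holds as a weakness of the secondary adjusted model. The p ≤ 0.20 screen selects by chance, leaves an unwritten choice whenever more than about 3 variables qualify, and nearly always drops one of the two allocation factors. The main consequence is an adjusted estimate that cannot be known in advance. The numerical effect of omitting GFR is small: an odds ratio drawn slightly toward 1 if GFR is prognostic, and about 0 to 2 points of power.

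The 0% admission figure needs a preferred-arm probability of about 0.7 or more and GFR tested as a category. The chance-entry figures for the whole candidate set rest on assumed numbers of independent variables; the 20% per variable does not. The change is worth making because it costs almost nothing and removes a data-driven choice, not because any primary result is in doubt.

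**What to change.** In F5.3, delete the p ≤ 0.20 rule and the between-arm baseline tests. Pre-specify the logistic model as arm, sex, GFR stratum (30–59, ≥ 60), access site and GP IIb/IIIa use. Enter GP IIb/IIIa use as the use intended at randomisation, if that is recorded. Report baseline characteristics descriptively, and limit the stratified tables to the three characteristics F5.3 already names, since their other trigger goes with the tests. Five variables need 5 × 10 = 50 bleeds under the plan's cap, so state now which term is dropped if fewer occur.

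The cost is SAP wording only. GFR stratum must already be known for every randomised patient because the allocation uses it. The one item to confirm is whether intended GP IIb/IIIa use is captured at randomisation.

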B.1.4 Aim 4 (Secondary): We aim to study the impact of sex, access-site (i.e., radial vs femoral), and concomitant use of glycoprotein (GP) IIb/IIIa inhibitors on the association of ACT target with bleeding. It has been shown that female sex is associated with higher ACT targets during PCI (17), and work from our group has shown an important observed interaction with myocardial infarction risk in women, but not men, with ACT targets >350 seconds(18). This observation of a potential differential sex-specific interaction has not previously been reported and requires validation in a prospective study. In addition, it has previously been shown that women appear to be at higher risk for developing forearm bleeding complications after transradial catheterization. The use of transradial PCI has steadily increased in the United States, though adoption of this technique remains lower than that observed in Canada and Europe. However, recent internal PCI data from the cardiac catheterization laboratory at Mayo Clinic Rochester has shown increasing utilization of the radial artery for PCI, now over 50%. At Mayo Clinic Florida, the percentage of radial access is over 70% and is considered the default access site for catheterization. It remains unknown whether ACT targets can be similarly interpreted for radial PCI, as these original targets were derived from studies in primarily transfemoral access cohorts with larger vascular access sheaths. Finally, the additional use of GP IIb/IIIa inhibitors in UFH-treated patients has been associated with higher rates of major and minor bleeding (9), thus lower ACT target values (i.e., 200-250 sec) are recommended in patients concomitantly treated with these agents. In the Mayo Clinic experience, there was no apparent interaction by GP IIb/IIIa inhibitor status when testing the association of ACT values to outcomes, however, baseline characteristics of groups receiving or not receiving these agents differed and residual confounding may have been present (18). The OPTIMAL-ACT trial will incorporate a pre-specified analysis with specific ACT targets in patients receiving GP IIb/IIIa inhibitors to better understand ACT targets and outcomes.

B.1.5 Aim 5 (Exploratory): We will explore the association of ACT targets with individual components of NACE and stent thrombosis for purposes of hypothesis generation.

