**Table 1. Summary of studies investigating association of ACT and outcomes**

Study	Year	Study Design	Patients (n)	Rates of adjunctive therapies	ACT associated with ischemic/thrombotic events?	ACT associated with bleeding?	Comments
Bittl et al 	1998	Post hoc analysis of clinical trial comparing heparin with bivalirudin	4,098	Balloon angioplasty only study, no thienopyridine, no GP IIb/IIIa inhibition	Higher risk of abrupt vessel closure in heparin-treated patients at lower initial ACT  No risk difference observed in bivalirudin treated patients	Bleeding requiring transfusion was not associated with initial ACT result, but was associated with peak ACT for both heparin and bivalirudin groups	ACT was only repeated if procedure>45 minutes or if patient developed intraprocedural ischemic complication (i.e, abrupt vessel closure)  Multivariable adjustment not performed
Chew et al 	2001	Meta analysis of pooled data from 6 trials of GP IIb/IIIa inhibitors	5,216	Majority of patients were angioplasty alone (<8% stenting), no thienopyridine	Reduction in composite ischemic events with increasing ACT, with optimal ACT range of 350 sec-375 sec  In subgroup of GP IIb/IIIa treated patients, there was no association between ACT and composite ischemic events across the ACT range of 275 sec to 375 sec	Peak ACT associated with bleeding, including higher rates of bleeding in patients additionally treated with GP IIb/IIIa inhibitors	Optimal ACT range did not vary when analyzed by procedural duration  Multivariable adjustment not performed
Tolleson et al 	2003	Post hoc analysis of clinical trial comparing heparin with eptifibatide	2,064	High rates of dual antiplatelet therapy (97%) and coronary stenting (97%)	No association between ACT at time of device activation and ischemic events (p=0.43). No increased risk of ischemic complications at low ACT values (as low as 200 sec).	No association between ACT and major bleeding (p=0.9). Higher ACT values associated with bleeding among GP IIb/IIIa treated patients	The lowest rate of ischemic events were seen in the lowest ACT tertile, with similar observation among GP IIb/IIIa treated patients  Lower-doses of weight-adjusted heparin used  Lower profile vascular devices

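### F5.4 compares NACE and bleeding components only by a trend test that is weak when the medium arm stands apart, plans no between-arm difference or interval, and does not name stent thrombosis

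*Combined protocol and SAP*

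**What the plan says.** F5.4 sets out one inferential method for the components: "We will explore the association of ACT target with individual components of bleeding and NACE using a Cochran-Armitage trend test". The same sentence also commits the trial to "report the number and percent of patients with each component separately for each group". The next sentence adds: "Adjustment for multiple testing will be conducted using the Holm step-down method". Trend scores, the size of the Holm family and its alpha are not given.

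Aim 5 (B.1.5) is wider in one respect: "We will explore the association of ACT targets with individual components of NACE and stent thrombosis for purposes of hypothesis generation". Stent thrombosis is not part of NACE, which F3.2.1 defines as the "composite of all-cause mortality, myocardial infarction (MI), stroke, target lesion revascularization, and major bleeding within 30 days after PCI". F3.2 places it next to NACE ("primary safety endpoint is a composite of net adverse clinical events (NACE) and stent thrombosis"), and Appendix II defines it separately. No paragraph of F5 names it.

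Elsewhere in F5.2, bleeding as a whole gets pairwise tests of medium and high against low, with relative risks and 95% intervals. NACE as a whole gets an interval per arm (Aim 2) and a Newcombe interval for low against high only (Aim 3).

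**The concern.** The stated objective is to find the best of three ACT target ranges. One possible answer is that the medium target is best, or worst, for ischemic events. A trend test over three ordered arms is built to detect a steady rise or fall, and it says little about a middle arm that departs from two similar outer arms.

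F5.4 is the only place where death, MI, stroke and revascularization are compared one by one. If the medium arm differed, the report would show raw counts beside an unremarkable p-value, with no estimate of the difference and no interval to show how much uncertainty remains. Stent thrombosis bears directly on whether a low target is safe, yet it would have no specified comparison at all.

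**Working it through.** **Inputs.** F.4 gives 504 patients, allocated 1:1:1, so n = 504/3 = 168 per arm. The documents give no component rates, so every rate below is an assumption. Table 2 offers some scale: NACE as a whole has a median of 12% (range 4% to 20%), and major bleeding runs from 1% to 3%. Scores 0, 1, 2 and, for the power figures, two-sided alpha 0.05 are also assumptions.

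**The plan's own figure.** F.4 claims more than 80% power for bleeding at 5% vs 15% and 5% vs 25%, each at 0.025. Simulation with 168 per arm and Pearson chi-square gives 81.1% for both tests together, so the figure reproduces. F5.4 states no power.

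**What the trend test measures.** With equal arms the mean score is 1, so

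- numerator: T = (0−1)·x_L + (1−1)·x_M + (2−1)·x_H = x_H − x_L
- variance: p̄(1−p̄)·n·[(−1)² + 0² + 1²] = 2n·p̄(1−p̄)
- z = (x_H − x_L) / √[2n·p̄(1−p̄)]

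The medium arm enters only through the pooled rate p̄.

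**Illustration: 17, 3 and 17 events of 168 (low, medium, high).**

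- Trend: x_H − x_L = 0, so z = 0 and p = 1.00.
- 2-df chi-square: p̄ = 37/504 = 0.0734; expected events per arm = 12.33; X² = [2 × 4.67² + 9.33²] / [168 × 0.0734 × 0.9266] = 130.7/11.43 = 11.43; p = exp(−11.43/2) = 0.003.
- Newcombe interval, low minus medium: 17/168 = 10.1% (Wilson 6.4% to 15.6%) and 3/168 = 1.8% (Wilson 0.6% to 5.1%). The difference is 8.3 points. Lower limit = 8.3 − √[(10.1−6.4)² + (5.1−1.8)²] ≈ 3.4. Upper limit = 8.3 + √[(15.6−10.1)² + (1.8−0.6)²] ≈ 13.9.

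The counts in the table would show this pattern. The planned test would not, and the interval that sizes it is not planned.

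**Power by simulation, 168 per arm, both tests at 0.05.**

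| Assumed rates low/medium/high | Trend | 2-df chi-square |
|---|---|---|
| 8/2/8% | 9% | 74% |
| 10/4/10% | 8% | 58% |
| 8/4/8% | 7% | 31% |
| 4/2/4% | 7% | 15% |
| 3/1/3% | 8% | 19% |
| 2/1/2% | 7% | 8% |
| 10/4/4% (harm in low arm only) | 63.8% | 63.9% |
| 8/5/2% (steady fall) | 73% | 63% |

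**Stent thrombosis, by text.** Aim 5 covers NACE components plus stent thrombosis. F5.4 covers components of bleeding and of NACE. F3.2.1 lists five NACE components, and stent thrombosis is not among them. Read literally, F5.4 therefore leaves it out. It is covered only if NACE in F5.4 is taken to mean the wider F3.2 composite, which the reader would have to guess.

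**The case against.** Several stronger readings are tempting, and the documents do not support them.

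- **That the plan would hide a best or worst medium arm.** F5.4 reports every component by group, so the pattern would be visible. Only the test is insensitive to it.
- **That Table 1 establishes a U-shape centred on the medium target.** One entry reads "Reduction in composite ischemic events with increasing ACT, with optimal ACT range of 350 sec-375 sec", but it comes from pooled trials with under 8% stenting, and three later entries report no ischemic association. Figure 1, which holds the arm ranges, was not in the text reviewed, so that range cannot be tied to the medium arm. The case rests on the stated objective alone.
- **That the trend test is the wrong choice.** The stated hypothesis is directional, and for a steady effect the trend test is the stronger one (73% vs 63%). For harm confined to the low arm, the 2-df test gains nothing.
- **That a 2-df test would solve the problem.** At 8/4/8%, a true doubling outside the medium arm, it has only 31% power. The headline case needs one component at 8%, two-thirds of the 12% median for all of NACE. For rare events the sample size is the limit.
- **That Holm is an error because it discounts harm signals.** It does cost power: at 10/4/4% the trend test falls from 64% to 36% at 0.05/7 and 28% at 0.05/14, which are first-step thresholds for assumed family sizes. Five NACE components plus up to nine bleeding grades ("hemorrhage grade of 1, 2, 3, or 5 or an EASY hematoma scale grade of I-V") would make 14. But Holm also limits false signals, and Aim 3 uses an unadjusted interval. This is a trade-off.
- **That stent thrombosis has been abandoned.** F3.2 and Aim 5 both retain it. The gap is one missing phrase in F5.4.

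What stands after all this is narrower: no difference or interval is planned for any component, the only test is nearly blind to one pattern that matters to the objective, and stent thrombosis is unnamed.

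**Conclusion.** The point holds as a worthwhile, low-cost improvement to an exploratory section. When the medium arm differs and the outer arms match, the planned test has roughly 7% to 9% power at the assumed rates. A 2-df test ranges from 74% (8/2/8%) down to 8% (2/1/2%). The more robust gain is therefore estimation: differences with intervals are informative whatever the shape, and F5.4 has none. The omission of stent thrombosis follows from the text and needs no assumption.

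The power figures rest on equally spaced scores, equal arms and assumed component rates. Unequally spaced scores would give the medium arm some weight. Neither the primary bleeding comparison nor the NACE non-inferiority conclusion is affected.

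**What to change.** In F5.4:

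1. Name stent thrombosis as an analysed outcome, in line with Aim 5.
2. Keep the trend test and state its scores.
3. For each NACE component and for stent thrombosis, report the low−high, low−medium and medium−high risk differences with unadjusted 95% Newcombe intervals, the method F5.2 already uses for Aim 3. Label them exploratory.
4. Add a 2-df chi-square or exact test as a supplement.
5. State the Holm family and alpha if Holm is kept for the trend p-values. Whether to keep it is the sponsor's choice.

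The cost is a few lines and one table, with no new data or patients. The downside is more unadjusted results: six outcomes with three intervals each make 18. One test at 0.05 on each of six outcomes would give at least one chance signal with probability of about 1 − 0.95⁶ = 26% if the tests were independent and held their nominal level. That is tolerable for hypothesis generation, provided the table says so.
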